6.4.2 Data to be collected at Exit

A complete follow-up examination should be documented for each subject on the date of exit. If the subject is lost to follow-up, the Exit-Lost To Follow Up form should be completed with the date of the last visit subject seen as the exit date.

6.4.3 Visit Requirements for Subjects Exited Prior to Study Completion

Subjects who discontinue the use of the assigned study lens for an adverse event or ocular findings must be followed as active subjects until the condition has resolved, returned to pre-study status or in the opinion of the licensed investigator warrants no additional follow-up as the outcome has become permanent.

If the subject must be followed beyond the 3 month study period, unscheduled visits must be conducted until the condition has resolved, returned to pre-study status or in the opinion of the licensed investigator warrants no further follow-up as the outcome has become permanent.

If the resolution has not occurred within 6 weeks following the study end-date, the subject will be exited from the study but must continue to be followed by the licensed investigator until the condition has resolved, returned to pre-study status or in the opinion of the licensed investigator warrants no further follow-up as the outcome has become permanent.

6.5 Adverse Event Reporting and Management

All Serious, Significant or Unanticipated Adverse Events must be reported to the Medical Monitor [REDACTED] within 24 hours of the licensed investigator initially becoming aware of the event.

Serious, significant or unanticipated adverse events, whether vision is impaired or not, will be documented in a written report and submitted by a licensed investigator to their respective Institutional Review Board with a copy sent to the Medical Monitor, by **fax, secure email with a receipt or express mail** within **ten (10)** working days of the licensed investigator initially becoming aware of the event.

Such a report will include a statement on whether or not the adverse event was considered study device related. The IRB can suspend or withdraw its approval if the cumulative data on adverse events indicates that continuation of the study is not appropriate for human subject safety.

Non-significant adverse events should be reported to the Medical Monitor within the normal timeframes for CRF submission and these will be included in a quarterly report to the Sponsor and the closeout report to the IRB at the conclusion of the study.

6.6 Criteria for Study Completion

Subjects will be counted as completed when they have completed the Month 3 visit of the study and have been exited from the study as Completed.

6.7 Medical Care for Subjects after Study Completion

No continuing medical care will be provided for subjects after study completion except for the care required to follow-up and resolve an adverse event that started during the study.

7 STUDY MONITORING

7.1 Monitoring Plans

A monitoring plan has been prepared for this study and is on file with [REDACTED] the study Sponsor.

7.2 Access to Source Data and Source Data Verification

The investigational site will allow the study monitor(s), sponsor representatives and/or authorized members of the IRB to observe procedures and inspect study records and subjects' medical records throughout the study to verify protocol compliance, case report completeness and investigational material accountability.

Should the investigator or investigational site be found to be non-compliant and unwilling or unable to convert noncompliant practices, it is the Sponsor's obligation to terminate that investigator's or investigational site's role in the investigation and the IRB will be notified.

8 STATISTICAL CONSIDERATIONS

8.1 Study Design, and Analytical Method

The primary objective of this evaluation is to provide evidence supporting substantial equivalence for the primary safety and efficacy variables of the Test Lens compared to the currently cleared and marketed Control Lens when used in a daily wear modality with an anticipated replacement period of approximately 30 days wear.

8.2 Sample Size Justification

The completed subjects sample size for this study is planned to be 50 Test Lens subjects and 25 Control Lens subjects based on a two to one (2:1) ratio of Test Lens subjects to Control Lens subjects.

The sample size for this study is based on the ISO 11980:2012 Ophthalmic optics – Contact lenses and contact lens care products – Guidance for clinical investigations.

Expected drop-out rates for both the Test and the Control lenses are calculated to be approximately 15%.

Due to the limited sample sizes required for this study the power calculations and level of significance are not appropriate for calculation. Differences between the results for the Test and Control cohorts will be evaluated based on clinical judgments.

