5.4.2 Efficacy Endpoints

The primary efficacy endpoint in this evaluation will be a comparison of the reported Snellen distance visual acuities as associated with the Test and Control lenses during scheduled visits. It is expected that the lens Snellen distance visual acuity results will be substantially equivalent between the Test and the Control lenses.

In addition, visual acuity with the Test and Control Lenses at the final study visit will be compared to the Test and Control Lens visual acuity at the Fitting visit. All changes ≥ 2 lines of visual acuity will be explained and compared across the Test and the Control lens groups. It is expected that the results will be substantially equivalent between the Test and the Control lens groups.

[REDACTED]

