8.3 Analysis & Procedures

Throughout the analysis of data, the results for each patient/eye will be used when available for summarization and analysis. All subject data will be considered for evaluation unless a significant protocol deviation was reported. Written justification will be required for the use of data in the evaluation of the safety and/or efficacy of study product from any subject or investigational site found to have a significant protocol deviation.

Summary analysis for all dispensed subjects will be presented, including completed and discontinued subsets of the Test and Control populations.

Descriptive statistics will be reported by cohort at baseline, fitting and follow-up. Continuous variables will be summarized using sample size (N), mean, standard deviation (SD), minimum and maximum, and categorical data variables will be summarized using the sample size, frequency distribution (count and percentage of subjects or eyes in each category), mean and standard deviation.

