8.4 Primary Safety Endpoint

The primary safety endpoints will be a comparison of the slit lamp findings and adverse events reported as associated with the Test lenses with those same findings reported as associated with the Control lenses by all scheduled and unscheduled follow-up visits. Slit lamp findings [REDACTED] are the primary indicators of safety issues with contact lenses.

[REDACTED]

Analysis of the results of the study will be based on a comparison of the differences in rates and degree of slit lamp findings between the Test and the Control lenses and the application of a clinical significance determination against the results. Clinical significance will be established through the average severity of the findings reported.

It is expected that the frequency and severity of the slit lamp findings and adverse events will be substantially equivalent between the Test and the Control lenses.

The following slit lamp findings will be presented and the frequency and average severity of findings by visit will be assessed.

- Epithelial Edema
- Stromal Edema
- Corneal Infiltrates
- Corneal Vascularization
- Corneal Staining
- Limbal Hyperemia
- Bulbar Hyperemia
- Palpebral Conjunctivitis
- Other Slit Lamp Findings

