8.5 Primary Efficacy Endpoint

The primary efficacy endpoint in this evaluation will be a comparison of the reported Snellen distance visual acuities as associated with the Test and Control lenses during scheduled visits. It is expected that the lens Snellen distance visual acuity results will be substantially equivalent between the Test and the Control lenses.

The visual acuity measurements will be recorded using a standard Snellen VA chart calibrated for an effective visual distance of 20 feet.

The visual acuity measurements will be analyzed using the relative comparative distribution of the visual acuity reports across the Test and Control lens groups.

In addition, the lens visual acuity at the final study visit will be compared to the over refractive lens visual acuity at the Training-Dispensing visit and the changes (≥ 2 line change) assessed and compared across the Test and the Control Lens groups. It is expected that the results of both analysis will be substantially equivalent between the Test and the Control Lenses.

[REDACTED]

[REDACTED]

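### Substantial equivalence is to be judged from within-arm summaries; the visible text plans no interval for any Test minus Control difference, although precision can be calculated at the planned sample size

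*Combined protocol and SAP*

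**What the plan says.** All references are to the combined protocol and SAP.

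- **8.1** gives the objective as to "provide evidence supporting substantial equivalence for the primary safety and efficacy variables" of the Test Lens compared with the cleared Control Lens.
- **8.2** plans 50 Test and 25 Control completers and gives the source: "The sample size for this study is based on the ISO 11980:2012". It then says "Due to the limited sample sizes required for this study the power calculations and level of significance are not appropriate for calculation", followed by "Differences between the results for the Test and Control cohorts will be evaluated based on clinical judgments".
- **8.3** lists the statistics to be reported by cohort. Continuous variables get N, mean, SD, minimum and maximum. Categorical variables get a "frequency distribution (count and percentage of subjects or eyes in each category"), with mean and SD.
- **8.4** compares the rates and degree of slit lamp findings: "Clinical significance will be established through the average severity of the findings reported".
- **8.5** says of efficacy: "The visual acuity measurements will be analyzed using the relative comparative distribution of the visual acuity reports across the Test and Control lens groups". Acuity changes of two lines or more are also compared; under 5.4.2 they "will be explained and compared across the Test and the Control lens groups".
- **8.7.6** defines a full analysis set of randomized subjects who were dispensed a lens, and analyzes discontinued subjects separately from completers.

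No confidence interval or standard error for a Test minus Control difference appears in the visible text of these sections.

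**The concern.** The objective is comparative, but every planned statistic describes one arm at a time. A cohort SD shows spread among subjects; it does not show how precisely the difference between arms is known. Two similar percentages do not tell the person judging them how large a Test excess the data still allow.

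This matters most for uncommon safety findings. There the arms can look identical, even at zero events each, while several percentage points of Test excess remain open. Followed as written, the plan could support a statement of equivalence without anyone having looked at that figure.

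The unit of analysis adds to the problem. Section 8.3 allows tabulation by subject or by eye, and an interval worked out from eye counts as if eyes were independent would be too narrow.

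**Working it through.** **Inputs from the documents.** Completers: 50 Test, 25 Control (8.2). Dispensed: about 60 and 30 (5.10). Drop-out: about 15% (8.2).

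**Assumptions.** The 95% level, the event counts and the event rates are mine; the documents give none. For means, results are in SD units because no SD is given.

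**1. The plan's own arithmetic.** Inflating completers for drop-out: 50/0.85 = 58.8, so 59; 25/0.85 = 29.4, so 30. This agrees with the stated 60 and 30 to within one subject. The 50 and 25 themselves come from the ISO guidance, so there is no power or precision calculation to reproduce.

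**2. Interval for a difference in percentages.** With p1, p2 the observed Test and Control proportions and (l, u) the Wilson limits in each arm, the Newcombe limits are

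- lower = (p1 − p2) − √[(p1 − l1)² + (u2 − p2)²]
- upper = (p1 − p2) + √[(u1 − p1)² + (p2 − l2)²]

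With no events, the Wilson lower limit is 0 and the upper limit is z²/(n + z²), with z² = 3.8415.

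- 0/60 v 0/30: u1 = 3.8415/63.8415 = 0.060, so the upper limit is +6.0 points.
- 0/50 v 0/25: u1 = 3.8415/53.8415 = 0.071, so +7.1 points.
- 6/60 v 3/30: Wilson limits are 0.0466 to 0.2015 and 0.0346 to 0.2562. The upper limit is √[(0.2015 − 0.1000)² + (0.1000 − 0.0346)²] = √(0.01030 + 0.00428) = 0.121, so +12.1 points.

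| Test v Control (subjects) | Observed difference | 95% Newcombe interval, points |
|---|---|---|
| 0/60 v 0/30 | 0 | −11.4 to +6.0 |
| 0/50 v 0/25 | 0 | −13.3 to +7.1 |
| 2/60 v 1/30 | 0 | −13.6 to +8.5 |
| 2/50 v 1/25 | 0 | −15.8 to +10.0 |
| 6/60 v 3/30 | 0 | −16.5 to +12.1 |

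**3. Precision that could be stated in advance.** Averaging the upper limit over the exact binomial distributions, with equal true rates in the two arms, gives the expected upper limit:

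| Assumed true rate | 60 v 30 | 50 v 25 |
|---|---|---|
| 3% | +8.3 | +9.4 |
| 5% | +9.5 | +10.6 |
| 10% | +12.0 | +13.2 |

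**4. Difference in subject-level means.** Half-width = t(0.975, n1 + n2 − 2) × SD × √(1/n1 + 1/n2).

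- 60 v 30: 1.987 × 0.2236 = 0.44 SD.
- 50 v 25: 1.993 × 0.2449 = 0.49 SD.

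**5. Eyes counted as independent.** At 0/120 v 0/60 eyes the upper limit is 3.8415/123.8415 = +3.1 points, against +6.0 for the same result counted by subject.

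**6. What the intervals would not do.** If the true Test rate were twice an assumed 5% Control rate, the lower limit would exceed zero in 5.8% of trials at 60 v 30 and in 3.5% at 50 v 25.

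**The case against.** The strongest reply is that this is a descriptive study sized from guidance, that 8.2 sets aside only power and a significance level, and that an interval is simply a statistic the plan did not list. Most of that stands. A reader might infer that 8.2 offers small numbers as a reason for not stating precision. It does not: it is silent on estimation, and its sentence on power and significance can remain.

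Second, the sections concerned carry redactions: blocks in 5.4.2, 8.4, 8.5 and 8.7.2, and 8.6 is not shown. Section 8.7.2 refers to efficacy criteria set out in the protocol, and these may lie in that text. An acceptance criterion would not by itself supply precision, but a redacted interval would answer the point. This limits confidence.

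Third, 8.7.5 says all data will appear in summary tables or listings, so a reader may be able to rebuild subject-level counts. The information is therefore not necessarily lost. The judgment planned in 8.2 would still be made without it.

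Fourth, intervals on every finding, visit and acuity level would add many derived outcomes with no stated position on multiplicity. That is fair, and it is why the fix below is short.

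**Conclusion.** The point holds for the visible text, with medium confidence because of the redactions. The plan seeks evidence of substantial equivalence and judges it clinically, without any measure of how precisely the arms are compared. At the planned numbers, identical observed results leave a Test excess of 6.0 to 12.1 points open at 60 v 30, for counts from 0/60 v 0/30 to 6/60 v 3/30. These figures rest on assumed counts and a 95% level, with one outcome per subject.

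Three stronger readings are not supported. The documents do not show that the sample size is wrong or that a formal equivalence test is required; a descriptive design is a legitimate choice. They do not show that any planned conclusion would change. Nor do they show that the acuity comparison is badly imprecise: dispensing requires 20/30 or better in each eye (5.10), so attainment of that level should start high. If all subjects kept it (60/60 v 30/30), the Test deficit not excluded would be 6.0 points. The gap is one of pre-specification and reporting, and it weighs most on uncommon safety findings.

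**What to change.** Keep the sample size, the endpoints, the clinical judgment and the 8.2 sentence on power and significance.

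**In 8.2**, add one sentence giving the expected precision at 60 v 30 and 50 v 25, using the figures in steps 3 and 4 with their assumptions.

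**In 8.3 to 8.5**, add descriptive two-sided 95% intervals for Test minus Control (Newcombe for percentages), with no multiplicity claim. Use the subject as the unit and the full analysis set of 8.7.6, completed and discontinued subjects together; the separate tables stay. Apply them to the percentage of subjects with:

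- (a) at least one adverse event;
- (b) each listed slit lamp finding in either eye, at the plan's clinically significant grade if the redacted text sets one, otherwise as an increase from the initial-visit grade. Section 5.10.4 excludes grades 2 to 4, so milder findings can be present at entry and should not count as new;
- (c) a lens acuity change of two lines or more at the final or exit visit, with the number who have no value. The reference visit must first be reconciled: 5.4.2 names the Fitting visit, 8.5 the Training-Dispensing visit.

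State the largest Test disadvantage that each interval does not exclude, and apply the clinical judgment to the interval. Do not treat the two eyes of a subject as independent. Intervals for average severity, the acuity distribution at each visit and mean logMAR are optional.

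**Cost.** SAP wording and modest programming; no added subjects or visits. The report will show openly that equivalence on uncommon safety findings is imprecise, and, as step 6 shows, the intervals will rarely detect a doubling of a low rate.

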8.3 Analysis & Procedures

Throughout the analysis of data, the results for each patient/eye will be used when available for summarization and analysis. All subject data will be considered for evaluation unless a significant protocol deviation was reported. Written justification will be required for the use of data in the evaluation of the safety and/or efficacy of study product from any subject or investigational site found to have a significant protocol deviation.

Summary analysis for all dispensed subjects will be presented, including completed and discontinued subsets of the Test and Control populations.

Descriptive statistics will be reported by cohort at baseline, fitting and follow-up. Continuous variables will be summarized using sample size (N), mean, standard deviation (SD), minimum and maximum, and categorical data variables will be summarized using the sample size, frequency distribution (count and percentage of subjects or eyes in each category), mean and standard deviation.

8.4 Primary Safety Endpoint

The primary safety endpoints will be a comparison of the slit lamp findings and adverse events reported as associated with the Test lenses with those same findings reported as associated with the Control lenses by all scheduled and unscheduled follow-up visits. Slit lamp findings [REDACTED] are the primary indicators of safety issues with contact lenses.

[REDACTED]

Analysis of the results of the study will be based on a comparison of the differences in rates and degree of slit lamp findings between the Test and the Control lenses and the application of a clinical significance determination against the results. Clinical significance will be established through the average severity of the findings reported.

It is expected that the frequency and severity of the slit lamp findings and adverse events will be substantially equivalent between the Test and the Control lenses.

The following slit lamp findings will be presented and the frequency and average severity of findings by visit will be assessed.

- Epithelial Edema
- Stromal Edema
- Corneal Infiltrates
- Corneal Vascularization
- Corneal Staining
- Limbal Hyperemia
- Bulbar Hyperemia
- Palpebral Conjunctivitis
- Other Slit Lamp Findings

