5.10.1 Subject History Inclusion Criteria

Prior to being considered eligible to participate in this study, each subject **MUST**:

1. Be at least 18 years of age as of the date of evaluation for the study.
2. **Have:**
 - a. **Read the Informed Consent Document**
 - b. **Been given an explanation of the Informed Consent Document**
 - c. **Indicated understanding of the Informed Consent Document**
 - d. **Signed the Informed Consent Document**
3. Be willing and able to adhere to the instructions provided by the investigational site and be willing and able to keep all specified appointments.
4. Be an adapted, frequent replacement, current full-time silicone hydrogel or soft contact lens wearer. An adapted full-time wearer is defined as wearing contact lenses at least 5 days per week for at least 8 hours per day for at least one month prior to participation in the study.
5. Possess or obtain prior to dispensing, wearable and visually functional (20/40 or better) eyeglasses.
6. Be in good general health, based on his/her knowledge.

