5.10.4 Ocular Health Assessment Exclusion Criteria

Does the subject have

1. Clinically significant (grade 2, 3 or 4) anterior segment abnormalities; or the presence of any infection of the eye, lids, or associated structures.
2. Pathological dry eye or associated dry eye symptoms with decreased tear levels and punctuate staining \geq Grade 2
3. Pterygium
4. Corneal scars within the visual axis
5. Neovascularization or ghost vessels \geq 1.0 mm in from the limbus
6. Giant papillary conjunctivitis of \geq Grade 2
7. Any inflammations such as anterior uveitis or iritis
8. Seborrheic eczema, seborrheic conjunctivitis or blepharitis

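### Section 8.4 shows no rule separating new or worsened slit lamp findings from grade 1 signs already present at entry, which exposes the any-grade rate and the average-severity judgment

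*Combined protocol and SAP*

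**What the plan says.** Section 5.10.1 requires each subject to "Be an adapted, frequent replacement, current full-time silicone hydrogel or soft contact lens wearer", which it takes to mean "wearing contact lenses at least 5 days per week for at least 8 hours per day for at least one month prior to participation". Sections 6.2 and 6.3 take subjects from the Initial visit to fitting and dispensing, and the visible text requires no lens-free interval.

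Section 5.10.4 excludes "Clinically significant (grade 2, 3 or 4) anterior segment abnormalities; or the presence of any infection of the eye, lids, or associated structures". For "Neovascularization or ghost vessels" the exclusion starts at 1.0 mm from the limbus. Some conditions are excluded at any grade, among them pterygium, scars in the visual axis, uveitis or iritis, and blepharitis. Section 5.10.2 also excludes a known history of corneal infiltrates or ulcer.

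Section 8.4 makes the primary safety endpoint a Test versus Control comparison of slit lamp findings and adverse events "by all scheduled and unscheduled follow-up visits". The slit lamp analysis is described as follows: "Analysis of the results of the study will be based on a comparison of the differences in rates and degree of slit lamp findings". Clinical significance is set by the average severity of what is reported, and frequency and average severity are tabulated by visit. A redacted block stands directly before this text.

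Section 8.3 adds: "Descriptive statistics will be reported by cohort at baseline, fitting and follow-up". Table 2 shows that the slit lamp form is completed at the Initial visit. For visual acuity, section 8.5 does use within-subject change from an earlier visit, counting changes of 2 lines or more.

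**The concern.** A grade 1 sign that the habitual lens left on the eye, and that is still there at a follow-up visit, enters the visible 8.4 tables in the same way as one that arose on the study lens. Such signs are expected in both arms alike, so they add a common background. That shrinks the absolute and relative contrast between lenses, towards the equivalence that the study sets out to support. With about 30 Control subjects the background may also differ between arms by chance, which can create or hide a difference.

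This matters more than usual because section 8.2 sets no significance level or power and leaves differences to clinical judgment. The tables are therefore the main evidence. The cohort summaries in 8.3 allow baseline and follow-up to be set side by side, but they cannot show which eyes worsened: equal prevalence at both times can hide new findings offset by resolved ones.

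**Working it through.** **1. The plan's own sample size.** Sections 5.10 and 8.2 give 50 Test and 25 Control completers, about 15% dropout, and 60 and 30 dispensed. 50/0.85 = 58.8, so 59; 25/0.85 = 29.4, so 30. The plan's 60 and 30 agree to within one subject. There is no power figure to reproduce.

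**2. What can be carried over.** An eligible eye has no clinically significant sign of grade 2 or higher at entry, so such a sign at follow-up is new or worsened. Exposure is confined to grade 1 signs and vessels under 1.0 mm. These touch staining, hyperemia, vascularization and palpebral findings on the 8.4 list.

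**3. Dilution.** Let b be the share of subjects with the sign at entry, q the share of those signs still present at the visit, and t and c the new-onset rates on Test and Control. All four are assumptions, since the documents give none. Raw rate = bq + (1 − bq) × onset, so raw difference = (1 − bq)(t − c). With t = 20% and c = 10% (true difference 10 points, ratio 2.0):

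| b | q | Raw Test | Raw Control | Difference (points) | Ratio |
|---|---|---|---|---|---|
| 10% | 25% | 22.0% | 12.25% | 9.75 | 1.80 |
| 20% | 25% | 24.0% | 14.5% | 9.5 | 1.66 |
| 20% | 100% | 36.0% | 28.0% | 8.0 | 1.29 |
| 50% | 25% | 30.0% | 21.25% | 8.75 | 1.41 |
| 50% | 100% | 60.0% | 55.0% | 5.0 | 1.09 |

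Among eyes clear of the sign at the Initial visit, the contrast is 20% versus 10% by construction. If new signs are counted over all eyes and can arise only in eyes that start clear, the ratio stays 2.0 but the difference is (1 − b) × 10: 8 points at b = 20% and 5 at b = 50%. The denominator must therefore be shown.

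**4. Chance imbalance at baseline, per subject.** SE = √[p(1 − p)(1/60 + 1/30)].
- p = 20%: SE 0.0894, 95% range ±17.5 points. Exact binomial chance of a gap of 10 points or more: 31%.
- p = 30%: SE 0.1025, ±20.1 points, 37%.
- p = 50%: SE 0.1118, ±21.9 points, 41%.

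At 50 versus 25 completers the ranges are ±19.2, ±22.0 and ±24.0 points.

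**5. How much of that gap reaches follow-up.** With the same new-onset rate c in both arms, follow-up gap = baseline gap × q × (1 − c). At c = 10%, a 10-point baseline gap becomes 10 × 0.25 × 0.9 = 2.25 points at 25% persistence, and 9 points at full persistence. The ±17.5 to ±21.9 range becomes about ±3.9 to ±4.9 points, or ±15.8 to ±19.7 points, respectively.

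**6. Average severity.** Illustration with assumed counts, averaging over reported findings: five new grade 3 findings average 3.0. Add twenty carried-over grade 1 findings and the average is (5×3 + 20×1)/25 = 1.4.

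**7. Ways to use the baseline for mean grade.** With baseline to follow-up correlation ρ (assumed), and relative to the raw comparison, the variance is 2(1 − ρ) for a change score and 1 − ρ² for regression adjustment.

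| ρ | Change score | Regression |
|---|---|---|
| 0.3 | 1.40 | 0.91 |
| 0.5 | 1.00 | 0.75 |
| 0.7 | 0.60 | 0.51 |

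A raw change score gains nothing at ρ = 0.5 and loses precision below it.

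**The case against.** The strongest reply has four parts.

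- **Redaction.** Text is blacked out in 8.4 just before the analysis sentence, and section 8.6.1 on secondary safety endpoints is in the contents list but not visible. A baseline rule may sit there. This stands: the point can only be that no visible rule exists. The absence of a washout is likewise read from silence.
- **Randomization.** Allocation is 2:1 at random, so habitual-lens signs balance in expectation. This stands against any claim of systematic bias. It does not remove dilution, or chance imbalance in a trial of this size.
- **Entry criteria.** With "Clinically significant (grade 2, 3 or 4) anterior segment abnormalities" excluded, the raw rate of grade 2 or higher is already close to an emergent rate. This stands, and it limits the point to the any-grade rate and the average severity.
- **Baseline is described.** An imbalance between arms would be seen in the 8.3 summaries. This stands in part, because those summaries do not link an eye to its own earlier grade.

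A reader might go further and infer that the comparison favors the Test lens, that the whole baseline gap persists to Month 3, or that vascularization will reflect the habitual lens throughout the 91 days. The documents support none of these: they give no prevalence, persistence or rate of change for any sign.

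**Conclusion.** The point holds for the any-grade frequency and the average-severity judgment in the visible 8.4. It does not extend to findings of grade 2 or higher, and it is not a bias in favor of one lens.

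Its size is uncertain. Under the assumed onset rates, a true 10-point difference shrinks to between 9.75 points (negligible) and 5.0 points, the latter only with 50% prevalence and full persistence. The baseline gap of about ±17.5 to ±21.9 points at 60 versus 30 rests on an assumed 20% to 50% prevalence. It is a baseline figure, not a distortion at follow-up. The change is worth making because the Initial grade is already collected and the plan already uses within-subject change for visual acuity.

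**What to change.** In section 8.4, add for each sign and visit, by arm, the count and percentage of eyes and of subjects with a new or worsened grade against the same eye's Initial-visit grade. Present these as shift tables by Initial grade, so that the denominator of eyes that started clear can be read off, and include a table of worst follow-up grade.

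State that clinical significance is judged on these tables together with the raw frequency and severity tables. If mean severity is compared between arms, adjust for the Initial grade by regression, allowing for two eyes per subject, rather than using a raw change score. If the redacted text already holds such a rule, a cross-reference is enough.

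Keep the raw tables: a count of changes alone would miss a grade 1 sign that was present at entry and that the study lens sustains. That limitation and some extra table output are the downsides. No added subjects, visits or examinations are needed.
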